## **4 STATISTICAL METHODS**

#### 4.1 Sample Size Justification and Power

#### 4.2 Overall Study Power

Using approximately 336 randomized participants (with a 1:1 assignment approximately 168 per arm), this study has at least 80% power to reject the null hypothesis of no efficacy in favor of the alternative that BHV4157 is efficacious, given the assumption of a difference in the mean change from baseline to 12 months between the BHV-4157 arm and placebo arm of 2.64 points on the ADAS-Cog 11 and 0.95 points in CDR-SOB, and under a range of interim effect sizes which give 93.7% probability of proceeding at the interim analysis.

This calculation assumes no more than a 26% dropout rate, which would leave  $336 \times 0.74 = 248$  subjects available at the final analysis, or 124 per arm. The calculation also assumes a standard deviation of 6 points on the change in ADAS-Cog 11 in each arm at both 6 months and 12 months, and a standard deviation of 2.3 points on the change in in CDR-SOB at 12 months; in addition a correlation of 45% between 12-month-change on the co-primary ADAS-Cog11 and CDR-SOB endpoints is assumed. These assumptions are supported by published retrospective data from historical ADCS studies. The computations use a 2-sided 2-sample t-test at 5% alpha to approximate power.

Briefly, the statistical reasoning is as follows:

- 1. P(pass overall) = P(pass final | pass interim) P(pass interim) ≥ P(pass final) P(pass interim)
- 2. P(pass final) = P(pass final ADAS) P(pass final CDR | pass final ADAS)
- 3. Numerical integration shows that P(pass final CDR | pass ADAS) is about 3% greater than P(pass final CDR), given the assumed 45% correlation between these endpoints.

Hence, if P(pass interim) = 0.937, P(pass final ADAS) = 0.92, and P(pass final CDR) = 0.90, then P(pass overall)  $\ge 0.92 \text{ x} (1.03 \text{ x} 0.90) \text{ x} 0.937 = 0.80.$ 

With 124 subjects per arm, the unconditional power for the ADAS-COG endpoint is 92%, if the mean difference in change is 2.64 points with standard deviation of 6 points within each arm. At this sample size, the unconditional power for the CDR-SOB endpoint is 90%, if the mean difference is 0.95 points with standard deviation of 2.3 points within each arm. Hence, if the interim analysis has power 0.937 or greater to pass, the overall power is 80% or more following the statistical reasoning given above.

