#### Subgroup Analyses

Except where indicated, descriptive statistics for the two co-primary endpoints ADAS-Cog 11 score and CDR-SOB score, and their change from baseline, will be tabulated by visit, separately, for the subgroups defined by:

- o Sex
- Mild vs Moderate MMSE status
- APOE e4 status
- Participation during Covid-19 (opportunity to complete randomization phase before March 13, 2020 vs on or after March 13, 2020)

As a further exploratory analysis, for Mild vs Moderate MMSE baseline status subgroups an MMRM analysis will be utilized on each subgroup using the model specification as described above.

In addition, descriptive statistics will also be presented by visit in the Open Label Extension Phase, by original randomized group (BHV-4157 and Placebo to BHV4157).

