Subjects who have a baseline MRI measure and at least one MRI evaluation on-treatment following baseline will form the mITT population for this analysis. The number of images which are not quantifiable due to scan alignment failure will be summarized by study arm. The percent deformation in volumetric MRI will first be analyzed using the mITT population via an analysis of covariance (ANCOVA) with baseline MMSE as a covariate based only on subjects with an assessment in the Week 48 analysis window as the main analysis. As an exploratory analysis, an additional analysis also using the same ANCOVA model, however including all subjects with a post-baseline assessment, will be conducted to compare between BHV-4157 and placebo based on subject's last post baseline MRI.

Finally, although only the last assessed post-baseline MRI deformation will be available at time of database lock, the MRI processing team will remain blind and will process the remaining post-baseline MRIs. A subsequent analysis utilizing all on-treatment post-baseline assessments will be done based on an MMRM analysis with the model including fixed effect terms for baseline MMSE score, visit, visit x baseline MMSE score interaction, and visit x treatment group interaction. Visit is treated as a categorical variable. A random effect will be included for

participant. The within-participant covariance will be unstructured. A similar approach to calculating degrees of freedom and convergence issues will be taken as done for the primary endpoint.

As a further exploratory analysis, for Mild vs Moderate MMSE baseline status subgroups an analysis will be utilized on each subgroup using the model specification as described above.

In addition, descriptive statistics will also be presented at endpoint in the Open Label Extension Phase, by original randomized group (BHV-4157 and Placebo to BHV4157).

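### Six efficacy endpoints are modelled separately in the mild and moderate MMSE strata, but the SAP plans no estimate or test of the difference in treatment effect between strata

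*SAP*

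**What the plan says.** Under Subgroup Analyses in SAP 4.8.3, sex, APOE e4 status and COVID-19 participation receive descriptive tables only. MMSE status also receives modelling: "for Mild vs Moderate MMSE baseline status subgroups an MMRM analysis will be utilized on each subgroup", using the primary model specification. SAP 4.8.4.2 (ADCS-ADL), 4.8.4.3 (NPI) and 4.8.4.4 (MMSE) repeat the instruction. For volumetric MRI, SAP 4.8.4.1 is less specific: "for Mild vs Moderate MMSE baseline status subgroups an analysis will be utilized on each subgroup". Its main analysis is a Week 48 ANCOVA with baseline MMSE as covariate.

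All of these analyses are labelled exploratory. The referenced MMRM (SAP 4.3.3 and 4.8.3; Protocol 12.3) has two interactions, visit by baseline score and visit by treatment. MMSE status enters as a main effect only and is the first term removed if the model fails to converge. Neither document specifies a treatment-by-MMSE-status term, a heterogeneity test, or an estimate of the between-stratum difference.

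**The concern.** The question a reader brings to a mild/moderate breakdown is whether the drug works differently in the two groups. Two separate models, each reporting an estimate, a confidence interval and a p-value, do not answer it. Each stratum holds only part of the sample, so with the same true effect in both, one p-value can easily fall below 0.05 and the other above it. Without a planned contrast, and without a sentence on how discordant strata are to be read, that pattern may be reported as an effect confined to one severity group. At stake is the interpretation of an exploratory result that could shape the population of a later trial.

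**Working it through.** **Inputs (SAP 4.2).** Test: "The computations use a 2-sided 2-sample t-test at 5% alpha to approximate power". Size: "with a 1:1 assignment approximately 168 per arm". Attrition: "This calculation assumes no more than a 26% dropout rate", leaving 124 per arm. ADAS-Cog 11: "if the mean difference in change is 2.64 points with standard deviation of 6 points within each arm". CDR-SOB: "if the mean difference is 0.95 points with standard deviation of 2.3 points within each arm". Correlation: "a correlation of 45% between 12-month-change on the co-primary ADAS-Cog11 and CDR-SOB endpoints is assumed". The mild/moderate split is my assumption: 50:50, range 30:70 to 70:30. I also assume equal SDs in the two strata and use two-sample approximations at Week 48.

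**1. The plan's own figures.** With 124 per arm, t-test power is 0.932 for ADAS-Cog 11 (stated 0.92) and 0.900 for CDR-SOB (stated 0.90). Joint power at correlation 0.45 is 0.857, and 0.857 x 0.937 = 0.803. The SAP's own product, 0.92 x 1.03 x 0.90 x 0.937, is 0.799. The stated 80% reproduces.

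**2. Power within a stratum, same true effect in both.** At 50:50 there are 62 per arm per stratum. Power is 0.681 (t) or 0.688 (normal) for ADAS-Cog 11, and 0.626 or 0.633 for CDR-SOB.

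**3. Exactly one stratum significant.** The strata contain different patients, so P = p1(1 - p2) + p2(1 - p1).
- ADAS-Cog 11, 50:50: 2 x 0.688 x 0.312 = 0.429 (0.434 with the t-test).
- CDR-SOB, 50:50: 2 x 0.633 x 0.367 = 0.465 (0.468 with the t-test).
- At 30:70 (37.2 and 86.8 per arm): ADAS-Cog 11, 0.475 x 0.174 + 0.826 x 0.525 = 0.516; CDR-SOB, 0.429 x 0.223 + 0.777 x 0.571 = 0.539.
- At half the assumed effect, 50:50: 0.36 and 0.33.

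**4. One favourable stratum while that endpoint's overall test is not significant.** At 50:50 the overall statistic is Z = (Z1 + Z2)/sqrt(2). Simulating Z1 and Z2 and counting cases with exactly one above 1.96 and |Z| below 1.96:

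| True effect in both strata | ADAS-Cog 11 | CDR-SOB |
|---|---|---|
| Full design effect | 1.6% | 2.3% |
| Half | about 8.5% | about 8.7% |
| None | 3.3% | 3.3% |

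**5. All 12 within-stratum tests (6 endpoints x 2 strata), no effect anywhere.** P(at least one favours drug) = 1 - 0.975^12 = 0.26 if independent. Under an assumed common correlation among the six endpoints, simulation gives about 20-21% at 0.45 and 16% at 0.7. The SAP states 0.45 only for the co-primary pair; applying it to all six, and the 0.7, are assumptions.

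**6. What a planned contrast would deliver.** SE of the between-stratum difference = SD x sqrt(2/n1 + 2/n2). At 50:50:
- ADAS-Cog 11: 6 x sqrt(4/62) = 1.52, 95% half-width 1.96 x 1.524 = 2.99.
- CDR-SOB: 2.3 x sqrt(4/62) = 0.584, half-width about 1.15.
- Power for a between-stratum difference equal to the whole assumed effect (2.64 or 0.95): 41% and 37%; at 30:70, 36% and 32%.
- False-positive rate for a claim that the strata differ: 5% per endpoint.

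With identical true effects, chance alone can therefore separate the stratum estimates by about 3.0 ADAS-Cog points (95% range), more than the 2.64 assumed for the trial.

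**The case against.** Much of the case on the other side stands.

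- The analyses are exploratory and outside the gatekeeping. SAP 4.3.4 adds that if the primaries fail, secondary-endpoint p-values are descriptive and no conclusions are drawn. Its separate descriptive-only sentence names exploratory endpoints, so it reaches the co-primary subgroup models only by analogy.
- Screening MMSE stratum is a randomisation factor, so each within-stratum comparison is itself valid. The gap lies only in comparing strata.
- The contrast can be recovered from planned output. The strata are disjoint, so the difference has SE sqrt(SE1^2 + SE2^2). It would be wrong to infer that the plan leaves no means of checking a differential claim; what is missing is the pre-specified line and its interpretation.
- A reader might take 43-47% as the chance of rescuing a failed trial with a subgroup claim. It is not: at the full design effect, most discordant cases come with a significant overall test on that endpoint. Step 4 gives the relevant figures.
- A reader might compute 1 - 0.95^12 = 46% for the 12 tests. That counts results favouring placebo, which could not support a claim of benefit in one stratum.
- MMSE status is constant within a stratum, but this does not invalidate the per-stratum MMRMs. The term is aliased and leaves the treatment estimate unchanged. It does not arise in the MRI ANCOVA, which uses baseline MMSE as a covariate.
- The interaction test is weak. That is true, and a reason to show the interval rather than omit the contrast.

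**Conclusion.** The gap is real but modest. The SAP plans separate stratum analyses for six endpoints and no comparison of the strata. With a common effect, discordant significance is close to an even chance: 43% and 47% at 50:50, up to 52% and 54% at 30:70. The narrower event, one favourable stratum with a non-significant overall test, occurs about 2%, 9% and 3% of the time per endpoint at full, half and no effect.

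These figures rest on the SAP's effects, SDs and attrition, the assumed split, and equal SDs across strata; MMRM covariate adjustment would shift the percentages without changing the conclusion. The documents do not support reading this as a threat to the primary result: primary type I error is unaffected. It is a low-priority improvement to an exploratory analysis.

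**What to change.** - For each MMRM endpoint, fit one exploratory model on the full mITT population, adding treatment x stratum, visit x stratum and treatment x visit x stratum to the primary specification.
- For the Week 48 MRI ANCOVA, add stratum and treatment x stratum only.
- Report the stratum-specific Week 48 effects and their difference, with 95% CI and interaction p-value, labelled exploratory.
- State that significance in one stratum alone is not evidence of a differential effect, and that a non-significant interaction does not show the effect is the same.
- If this model fails to converge, keep MMSE status and go straight to the alternative covariance structures; the primary rule of dropping MMSE status first would remove the factor under study.
- If the per-stratum MMRMs are also kept, drop MMSE status from them.

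The cost is one extra model per endpoint, with no new data and no change to the primary analysis. The downside is imprecision: intervals of about +/-3.0 ADAS-Cog and +/-1.15 CDR-SOB points at 50:50, and power of about 41% and 37% even for a between-stratum difference as large as the whole assumed effect.

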#### 4.8.4 Secondary Efficacy Endpoints

#### 4.8.4.1 Volumetric MRI

Bilateral hippocampal volume (as well as the exploratory endpoints of bilateral lateral ventricles and whole brain volume) will be measured as volumetric MRI. MRI imaging of the brain will be performed in order to measure brain atrophy over time. Results from vMRI studies suggest that the patterns of atrophy in AD can reliably be detected and tracked across time. Atrophy of the medial temporal lobe, including hippocampus and entorhinal cortex, has long been described in vMRI studies of AD. Hippocampal volume derived from MRI correlates with histological hippocampal volume and degree of neuronal loss and AD pathology, and entorhinal cortical thickness change appears to be an early and sensitive indicator of neurodegeneration associated with AD. Longitudinal MRI measures of regional and whole brain volumetric change provide a valuable complement to cognitive measures in that they are not influenced by temporary symptomatic improvements, and they provide an early index of the study drug's ability to reach the target organ and have an effect on AD-related atrophy.

The analysis of structural change will be performed through Quarc nonlinear registration (see Holland et al., 2011) comparing each participant's follow-up scan to the initial baseline scan. For the interim analysis, the week 24 scan will be registered to the baseline scan, and for the final analysis, the latest timepoint scan will be registered to the baseline scan. The procedure provides percent deformation within regions of interest (ROIs) obtained through segmentation of the baseline scan. The registration of serially-acquired brain volumes yields a deformation field that represents the volumetric shift of internal structure required for optimal overlaying of the two scans. The anatomically-based segmentation is overlaid on the smoothed voxel-wise deformation field and an average percent deformation is created for each ROI. Visual QC of registration is performed and values from scans passing QC are returned to the statistical team for analysis.

This treatment effect will be mean difference in change in volumetric MRI, compared between the BVH-4157 and placebo groups.

Subjects who have a baseline MRI measure and at least one MRI evaluation on-treatment following baseline will form the mITT population for this analysis. The number of images which are not quantifiable due to scan alignment failure will be summarized by study arm. The percent deformation in volumetric MRI will first be analyzed using the mITT population via an analysis of covariance (ANCOVA) with baseline MMSE as a covariate based only on subjects with an assessment in the Week 48 analysis window as the main analysis. As an exploratory analysis, an additional analysis also using the same ANCOVA model, however including all subjects with a post-baseline assessment, will be conducted to compare between BHV-4157 and placebo based on subject's last post baseline MRI.

Finally, although only the last assessed post-baseline MRI deformation will be available at time of database lock, the MRI processing team will remain blind and will process the remaining post-baseline MRIs. A subsequent analysis utilizing all on-treatment post-baseline assessments will be done based on an MMRM analysis with the model including fixed effect terms for baseline MMSE score, visit, visit x baseline MMSE score interaction, and visit x treatment group interaction. Visit is treated as a categorical variable. A random effect will be included for

participant. The within-participant covariance will be unstructured. A similar approach to calculating degrees of freedom and convergence issues will be taken as done for the primary endpoint.

As a further exploratory analysis, for Mild vs Moderate MMSE baseline status subgroups an analysis will be utilized on each subgroup using the model specification as described above.

In addition, descriptive statistics will also be presented at endpoint in the Open Label Extension Phase, by original randomized group (BHV-4157 and Placebo to BHV4157).

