10 EARLY DISCONTINUATION/WITHDRAWAL PROCEDURES

The entire study may be discontinued at the discretion of ADCS or Biohaven. In these circumstances the Investigator will arrange for all ongoing participants to be seen and for their study medication to be discontinued as soon as is safely possible.

Participants are free to withdraw from study participation at any time, for any reason, and without prejudice.

Discontinuation of study treatment and/or the participation of an individual participant in the study will be terminated in the following circumstances:

- Withdrawal of informed consent by the participant or LAR. If the study partner withdraws
 his/her consent to participate then attempts will be made to find a replacement. In any event
 the participant will be continued in the study in so far as possible. Participants who
 withdraw consent will be advised by the Investigator regarding subsequent treatment and
 investigation.
- Treatment of a participant with a non-permitted concomitant medication may necessitate discontinuation from study medications, and will be determined by the Investigator in conjunction with the Medical Monitor.
- Adverse event or other significant medical condition which, in the opinion of the Investigator render it necessary to discontinue study medication.
- The participant experiences a medical emergency that necessitates unblinding their treatment assignment. (See Section 6.6).
- Any other occurrence that, in the Investigator's opinion, makes continued participation contrary to the participant's best interests.
- Movement of participant into a long-term care nursing facility. Movement into an assisted living facility is not cause for discontinuation from the study.

Participants who discontinue active treatment for any reason will have the opportunity to continue on the protocol with further visits per protocol to the end of the double-blind phase of the study with their ongoing consent. Their continued participation will be encouraged.

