 - Week 24 and week 48 vMRI: the protocol window for vMRI at week 24 and week 48 is 14 days before and up to 14 days after the clinic visit. If participant is terminating early at 36 week or after, obtain vMRI if MRI is performed on the same day as a lumbar puncture at week 48, the vMRI must be conducted before the lumbar puncture. Otherwise, at least a 3-day window between vMRI and the lumbar puncture is required.
- 12 It is anticipated that lumbar puncture will be performed on an estimated 100 study participants as part of a sub-study (separate informed consent required).
- Only for the CSF sub-study. Visit windows for CSF are: up to 14 days prior to first dose of study medication and up to 14 days prior to weeks 24 and 48. If a participant in the CSF sub-study is terminating early, they do not need to undergo lumbar puncture.
- Post lumbar puncture safety follow up telephone call must occur 1 to 3 days after the lumbar puncture is performed.
- First dose of study medication will be given in the clinic at the baseline clinic visit after completion of the baseline visit procedures.
- Participants will receive a phone call during Week 2 from site study personnel in order to assess study drug tolerability. If tolerable, then the participant will be instructed to proceed with dose escalation.
- 17 Treatment blinding questionnaire to be administered to site PI and Raters.

Table 3: Schedule of Assessments and Events – Open-Label Extension Phase

Visit Number	1	2	3	4	5	6	7	8	9	10	
Study Visit Timepoint	Baselinel	Abbrev- iated Drug Dispensat ion Visit ²	Ext Week 2 (+/- 7 days)	Ext Week 4 (+/- 7 days)	Ext Week 8 ³ (+/- 7 days)	Ext Week 12 (+/- 7 days)	Ext Week 24 (+/- 7 days)	Ext Week 36 (+/- 7 days)	Ext Week 48 or Early Term (+/- 7 days)	Week2 Post last dose (+/- 7 days)	Unsched- uled Visit ⁴ (+/- 7 days)
Informed Consent	X	X									
Medical History	X										
Adverse Event Assessment	X	X	X	X	X^3	X	X	X	X	X	X
Telephone Check-in ⁵ Includes AE assessment and concomitant medication review			X		X ³						
Laboratory Assessments ⁶	X			X	X^3	X	X	X	X		
Urinalysis	X						X		X		
Physical Exam	X								X		
Physical Measurement - Weight	X						X		X		
Vital Signs	X	X		X		X	X	X	X	X	X
12-Lead ECG	X					X	X		X		
Concomitant Medication Review	X	X	X	X	X	X	X	X	X	X	X
Sheehan Suicidality Tracking Scale (S-STS)	X	X		X		X	X	X	X	X	
Dispense Study Drug	X	X		X		X	X	X			
Volumetric MRI ⁷	X								X		
ADAS-Cog 11	X						X		X		
CDR-SOB	X						X		X		

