#### Summary of primary estimand:

The effect relative to placebo of treatment as actually taken for 48 weeks during the doubleblind phase, in the protocol-defined mITT study population.

1. Objective

An estimate of efficacy which would potentially be supportive of registration; thus similar to an ITT, "as taken" estimand.

- 2. Estimand
  - A. The population is the mITT population as defined by the protocol's inclusion and exclusion criteria.
  - B. Efficacy is measured by the change from baseline to 48 weeks in the co-primary endpoints (ADAS-cog and CDR-SOB)
  - C. The treatment evaluated is the randomized treatment as it was assigned to study subjects. All types of intercurrent events are incorporated using a treatment policy strategy, which evaluates the randomized treatment as taken including missed or modified doses, drug discontinuation, and concurrent treatments. Study dropout including those potentially related to the COVID-19 pandemic (and corresponding discontinuation of assessments) will be handled by a hypothetical strategy to estimate what the outcome would have been at the designated time point if all subjects were continued to be assessed. Deaths are not expected during the 48 week double-blind phase follow-up in the enrolled subject population.

- D. The mean change from baseline between treatment and control arm on the 2 endpoints will be compared at 48 weeks between treatment and placebo arms. A significant difference in both endpoints at familywise error rate of 5% will be required for success.
- 3. Primary estimator and missing data.

The estimator is a MMRM using all available assessments. Under the assumption that data are MAR conditional on model covariates and observed assessments, this analysis estimates the treatment as taken in the mITT study population.

Note that MAR assumes that subjects will follow the same trajectory after dropping out of the study as while on the study, conditional on the model covariates. However, if subjects tend to preferentially drop out after discontinuation of study drug, their post-dropout trajectory (off treatment) may differ from their pre-dropout trajectory (on treatment). In this case the MAR assumption may not hold. A sensitivity analyses is proposed to assess this scenario.

4. Sensitivity analyses and missing data.

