# Table 2:Analysis Windows for All Other Efficacy Parameters Including NPI,
ADCS-ADL, MMSE, MoCA, Volumetric MRI, CSF Biomarkers and
Blood Biomarkers and NACC measures in the 48 week
Randomization Phase.

Evaluation	Protocol-Specified Day	Analysis-Specified Interval
Randomization Phase		
Week 24	Day 168	Day 2-252
Week 48	Day 336	Day 253-420

Note: Baseline assessment will be defined as the last available assessment on or before first day of randomization phase study drug. Days based on days from first day of randomization phase study drug.

Table 3:	Analysis Windows for Safety Parameters: Sheehan Suicidal
	Tracking, Vital Signs, Lab Assessments, PK and ECG

Evaluation	Protocol-Specified Day	Analysis-Specified Interval
Randomization Phase		
Week 4	Day 28	Day 2-42
Week 8	Day 56	Day 43-70
Week 12	Day 84	Day 71-98
Week 16	Day 112	Day 99-126
Week 20	Day 140	Day 127-154
Week 24	Day 168	Day 155-182
Week 28	Day 196	Day 183-210
Week 32	Day 224	Day 211-238
Week 36	Day 252	Day 239-266
Week 40	Day 280	Day 267-294
Week 44	Day 308	Day 295-322
Week 48	Day 336	Day 323-420

Note: Baseline assessment will be defined as the last available assessment on or before first day of randomization phase study drug. Days based on days from first day of randomization phase study drug.

If a participant has more than one record within an analysis window, the latest record within the window will be used in the analysis.

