#### 4.4 Analysis Periods and Study Phases

Analysis periods and study phases are defined as follows:

- Screening Phase: will include all assessments on or before the first day of study drug.
- On-Treatment in Randomization Phase (Safety Assessments): except where indicated, "ontreatment" in the Randomization Phase will include all assessments after first day of study drug and up to the first day of dosing of the Open Label Extension Phase study drug (for subjects entering extension) or up to the last day of Randomization Phase study drug + 30 days, whichever comes first. For AEs, "on-treatment" in the Randomization Phase will include first day of dosing of the Randomization Phase study drug up to the last day of Randomization Phase study drug + 30 days for those not going into the Extension Phase or up to the day before the first day of dosing of Extension Phase medication for those subjects who do.
- On-Treatment in Randomization Phase (Efficacy Assessments): except where indicated, "on-treatment" in the Randomization Phase will include all assessments after first day of study drug and up to the first day of dosing of the Open Label Extension Phase study drug (for subjects entering extension) or up to the last day of Randomization Phase study drug + 3 days, whichever comes first.
- On-Treatment in Open Label Extension Phase (Safety Assessments): except where indicated, "on-treatment" in the Open Label Extension Phase will include all assessments after first day of open label study drug and up to the last day of Open Label Extension Phase study drug + 30 days. For AEs, "on-treatment" in the Open Label Extension Phase will include first day of dosing of the Open Label Extension Phase study drug up to the last day of Open Label Extension Phase study drug up to the last day of Open Label Extension Phase study drug + 30 days.
- On-Treatment in Open Label Extension Phase (Efficacy Assessments): will include all efficacy assessments after the first day of dosing of OL Extension Phase study drug to the

last day of study drug +3 days. Baseline for the extension will be the last available assessment on or before the first day of dosing of OL Extension Phase medication.

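### The Holm-tested hippocampal MRI analysis admits only participants with an on-treatment follow-up scan, an adherence-based exclusion that the protocol and SAP mITT do not contain

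*SAP*

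**What the plan says.** **Population.** SAP 4.8.4.1 states: "Subjects who have a baseline MRI measure and at least one MRI evaluation on-treatment following baseline will form the mITT population for this analysis". Its main analysis is an ANCOVA of percent deformation in that population, limited to those with a scan in the Week 48 analysis window. SAP Table 2 sets that window at Day 253 to 420.

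**Meaning of on-treatment.** For efficacy data in the Randomization Phase, SAP 4.4 ends the period at the first open-label dose "or up to the last day of Randomization Phase study drug + 3 days, whichever comes first". MRI falls under this rule and not the 30-day safety rule, because it is named in Table 2, whose title begins "Analysis Windows for All Other Efficacy Parameters Including NPI".

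**Later MRI analyses.** An exploratory ANCOVA takes all subjects with a post-baseline scan and uses the last one. After database lock, once the remaining scans have been processed: "A subsequent analysis utilizing all on-treatment post-baseline assessments will be done based on an MMRM analysis".

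**Scan timing and follow-up.** Protocol Appendix I (Table 1, footnote 11) says "the protocol window for vMRI at week 24 and week 48 is 14 days before and up to 14 days after the clinic visit". Protocol Section 10 says "Participants who discontinue active treatment for any reason will have the opportunity to continue on the protocol with further visits per protocol", up to the end of the double-blind phase.

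**Multiplicity.** Hippocampal volume, NPI, ADCS-ADL and MMSE form the Holm family (Protocol 12.4; SAP 4.3.4).

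**The concern.** Whether a participant is still on drug when scanned is known only after randomisation and may depend on treatment. Making it a condition of entry means that the two arms compared are no longer the arms as randomised. The general mITT set in Protocol 12.2 and SAP 3.1 requires at least one dose, a baseline and a post-baseline efficacy evaluation; it does not ask whether the participant was still taking drug.

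The condition applies to an endpoint on which a formal claim can be made if both co-primaries succeed. One member of the Holm family would then rest on an adherence-selected set and the other three on the general mITT set. SAP 4.8.4.1 values MRI as a measure of atrophy that short-lived symptomatic change does not affect, and it gives no reason for cutting off scans 3 days after the last dose.

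**Working it through.** The readable text gives no power or sample size for the MRI endpoint, so there is no planning figure for it to reproduce. The check sets the passages side by side and then adds an illustrative count.

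**Step 1: who can be treated as off-treatment.** Protocol Section 10 keeps participants who stop drug in follow-up, so scans taken well after the last dose are foreseen. A permitted scan can also fall outside the limit for a participant who took every dose. The scan window runs from day −14 to day +14 around the visit, 29 days in all. If the last double-blind dose is on the Week 48 visit day, days +4 to +14 (11 days) lie beyond last dose + 3.

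**Step 2: who leaves the main ANCOVA.** A participant needs (i) a baseline scan, (ii) at least one on-treatment post-baseline scan and (iii) a scan on Day 253 to 420.

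| Participant | (ii) | (iii) | Main ANCOVA |
|---|---|---|---|
| On drug at a usable Week 24 scan; Week 48 scan on day +10 | met | met | kept |
| Stopped drug more than 3 days before any follow-up scan; scanned at Week 48 | not met | met | lost |
| No usable Week 24 scan; Week 48 scan permitted but more than 3 days after last dose | not met | met | lost |

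**Step 3: what leaves the MMRM.** That model uses on-treatment scans only. It therefore also omits every permitted scan taken more than 3 days after the last dose, including the one in the first row.

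**Step 4: comparison with the rest of the plan.**
- Protocol 12.2 and SAP 3.1 make the general mITT set primary for all efficacy analyses, with no on-treatment condition.
- For the primary estimand, SAP 4.3.1.1 says "All types of intercurrent events are incorporated using a treatment policy strategy", and it counts drug discontinuation among those events.
- SAP 4.8.4.2 to 4.8.4.4 analyse ADCS-ADL, NPI and MMSE in the mITT set, again with no on-treatment condition.
- SAP 4.8.3 uses on-treatment data for the co-primaries only in a supplemental analysis.

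**Step 5: illustrative size.** The documents do not give the inputs, so these are assumptions:
- *a*, off drug more than 3 days before the Week 24 scan but still followed to a Week 48 scan: 0 to 10%.
- *b*, among the rest, no usable Week 24 scan: 0 to 10%.
- *c*, among those, Week 48 scan more than 3 days after last dose: 10 to 40%.

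The base is the planned number at the final analysis: 336 × 0.74 = 248.64, stated as 248, or 124 per arm. The excluded fraction is *a* + (1 − *a*) × *b* × *c*.
- Low: 0 + 1 × 0 × 0.10 = 0, so 0 of 124.
- Middle: 0.05 + 0.95 × 0.05 × 0.25 = 0.0619, so 7.7 of 124.
- High: 0.10 + 0.90 × 0.10 × 0.40 = 0.136, so 16.9 of 124.

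In the high case, 12.4 of the 16.9 come from *a*, the participants who stopped drug but stayed.

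**The case against.** **The rule may lose few people or none.** One on-treatment Week 24 scan is enough to qualify, and the range above includes zero. This stands, and it limits the size of the point. It does not remove the conflict over who belongs in the population.

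**On-treatment may not mean last dose + 3 days here.** SAP 4.8.4.1 does not cite SAP 4.4, which allows for exceptions. The visit-window tables sit under a heading that itself calls them on-treatment, and they run to Day 420. Against this, SAP 4.4 is the only place that defines the term for efficacy data, SAP 4.8.3 repeats the 3-day limit for the co-primaries, and the tables only allocate scans to visits. At most the text is ambiguous, and that also calls for a correction.

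**An unrestricted ANCOVA is already planned.** Its own wording takes all subjects with a post-baseline scan, so it can cover those excluded. But it is exploratory, and by using the last scan it mixes Week 24 with Week 48. It does not repair the Holm test.

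**Secondary endpoints need not share the primary estimand.** Treatment policy is specified for the primary estimand, SAP 4.3.1 promises only a similar strategy for the secondaries, and Holm does not require a common estimand. All of this is correct: Holm's control of type I error does not depend on it. The conflict with the protocol's population for all efficacy analyses remains, and the SAP gives no reason for treating MRI differently.

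**Conclusion.** The point holds as an inconsistency of population. Followed literally, SAP 4.8.4.1 puts an adherence-dependent, post-randomisation exclusion into a Holm-tested endpoint, and a wording change removes it. This rests on reading on-treatment as SAP 4.4 defines it, and on the main ANCOVA being the analysis that carries the Holm test. The number affected and the direction of any bias cannot be computed from the documents. The 0 to 17 per arm is arithmetic on assumed inputs and not a forecast.

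A reader might infer three stronger things, none of which the documents support:

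- *That late Week 48 scans are lost from the Holm test, at 11 of 29 days (38%).* Such a scan stays in the main ANCOVA if the participant has an on-treatment Week 24 scan; only the later MMRM drops it. The 38% is also a share of calendar days. Nothing says that scans are spread evenly over the window, so it gives no basis for a loss of precision.
- *That the Week 48 scan must itself be on-treatment, since only the last scan is quantified at lock.* The population sentence asks for at least one on-treatment evaluation, and the main-analysis sentence asks only for a scan in the Week 48 window.
- *That the exclusion will differ by arm.* The ataxia study in Protocol 1.7.1.1 had 7 of 71 non-completers on active and 2 of 70 on placebo, and adverse-event withdrawal from drug in 3 of 71 and 0 of 70. That was another disease, at 140 mg for 8 weeks, and non-completers are not people who stop drug, stay and are scanned. A difference here is possible but not shown.

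**What to change.** Before unblinding, amend SAP 4.8.4.1:

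1. Define the MRI population by a baseline scan and at least one post-baseline scan in the double-blind phase, with no on-treatment condition.
2. Use all double-blind-phase scans regardless of drug status, in the main ANCOVA (those in the Week 48 window) and in the MMRM.
3. Keep an on-treatment version as a supplemental analysis, as SAP 4.8.3 does for the co-primaries.
4. Keep the first open-label dose as the end of double-blind MRI data, or use later scans only in a sensitivity analysis. After that dose, former placebo participants are on active drug.
5. Make the same population change in SAP 4.8.5.4, where the biomarker analysis has the same condition.

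The scans are already scheduled, so the cost is SAP wording and programming. The downside is that a few off-drug scans enter the main analysis, which could dilute an effect that depends on continued dosing. The plan already accepts this for the co-primaries and the other three secondaries, and the supplemental analysis would still show the on-treatment result.
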